3D Time-of-Flight Magnetic Resonance Angiography in Hemodialysis Patients With
Arteriovenous Fistula

Clinical trial No: NCT04312731

Date:2022-1-4

Study Design and Patient Population

From June 2018 to March 2021, maintenance dialysis patients in the nephrology department at our hospital with suspected dysfunctional AVFs were considered candidates for this study. The inclusion criteria of the dysfunctional hemodialysis access patients were as follows. 1) Physical examination showed swelling of the extremities, a reduction of pulsation and a tremor at the anastomotic site, and reduction of the murmur. 2) The venous pressure and arterial negative pressure were increased, and the blood flow of the fistula was decreased (< 500 mL/min). 3) The hemodialysis site was difficult to puncture during dialysis; the cannulation coagulated easily; and the bleeding time was prolonged after needle extraction. The exclusion criteria were as follows: 1) a previous history of stent or artificial blood vessel implantation; 2) contraindications to magnetic resonance; 3) a platelet (PLT) level $< 60 \times 10^9$ /L or an international normalized ratio (INR) > 1.5 ; 4), pregnancy or lactation; and 5) a functional failure of other important organs or other serious diseases except for renal failure (Clinical trial No. NCT04312731). A detailed flowchart of the patient selection process is provided in Figure 1.

Imaging protocol

Color Doppler ultrasonography: Ultrasonography studies were independently performed in the Department of Ultrasonography by two sonographers ([name] and [name] with 12 and 8 years of experience, respectively). The entire hemodialysis access fistula was evaluated by means of 5- and 7-MHz linear array scanners (Aspen Advanced; Siemens, Erlangen, Germany), from the feeding artery from the level of the axillary

artery and draining vein to the level of the subclavian vein. The examinations were performed in both longitudinal and transverse planes. Spectral waveforms were obtained at each examination level, and color Doppler interrogation was used throughout the studies. Peak systolic velocity (PSV) and the location of any narrowed areas were calculated and recorded. The PSV criteria were the same for the inflow, shunt proper (e.g., anastomotic sites), and outflow tract. All measurements were obtained from waveforms with an insonating angle of less than 60° when possible. The stenosis was considered significant if the PSV was greater than 375 cm/s or if there was narrowing of 50% or more on the grayscale imaging. All data were recorded on a form on which the localizations of the stenoses were drawn.

Magnetic resonance angiography: MRIs were undertaken on a 3-T system (Skyra, Siemens Healthcare, Erlangen, Germany) using a superficial body array matrix coil. The imaging was performed with the patient lying supine, with the target arm containing the fistula as close to the midline of the examination bed as possible. A TOF-MRA acquisition, covering a transverse slab from the elbow joint to 5 cm below the anastomosis, had acquisition parameters of a 23 ms/3.5 ms repetition time/echo time; a 70° flip angle; a 200*200 *200 mm³ volume of interest; a 2 mm section thickness; a 1024*1024 acquisition matrix; 180 slices and an appropriately 5 minutes scan duration. Based on the TOF images, two radiologists, with extensive experience in AVF diagnosis, preliminarily determined the position of the stenosis. Finally, through an automatic subtraction method, maximum-intensity projection (MIP) images of each of the four stations were reconstructed in the coronal orientation and were fused to form a single

image using MR MobiView software (Philips Medical Systems).

The *DSAs* were carried out by interventional radiologists ([name] and [name], who have 17 and 15 years of experience in vascular imaging, respectively) on the digital angiography unit (Artis zee; Siemens Medical Solutions), within a mean of 10 (range: 1-14) days after the ultrasonography and MRA. An access approach on the brachial artery was used. An iodine-based contrast agent (Imeron 350; Bracco Imaging, Shanghai, China) was injected through a 5-French catheter positioned in the feeding artery. The anteroposterior views were chosen at the discretion of the interventional radiologist. Images of the feeding artery, fistula and distal venous outflow were obtained. After the angiogram, percutaneous transluminal angioplasty (PTA) was performed for the areas that had >50% stenoses or that had a total occlusion.

Image analysis

Two radiologists ([name] and [name] with 10 and 15 years of experience in evaluating vascular images, respectively) independently evaluated the MRA and DSA images while blinded to the patient's identity, medical history, and symptoms. In case of disagreement, consensus was reached after mutual consultation. The MRA datasets were evaluated on dedicated workstations (Syngo® MR B17, Siemens), and the DSA images were also analyzed on a workstation (SyngoXWP; Siemens Healthcare).

The image quality and diagnostic performance of TOF-MRA were evaluated in all regions. For all participants, the architecture of the AVF was divided into three regions: arterial inflow, anastomosis (including 1 cm of vessel length on both sides of the anastomosis), and venous outflow. The most central part of the venous outflow,

comprising the proximal half of the brachiocephalic vein and superior caval vein, was excluded from the analysis because these venous structures were not depicted by the TOF-MRA in this study.

The diagnostic quality of the images obtained at each of the three regions was graded (0-4) using the Likert scale: 0 for a “nondiagnostic” image; 1 for a “poor” quality, with the observer not confident due to severe image artifacts, significant venous contamination and/or poor vascular signals; 2 for a “fair” quality, with the observer marginally confident due to minor artifacts, mild-to-moderate venous contamination and/or a moderately homogenous vascular signal; 3 for a “good” quality, with the observer being confident; or 4 for an “excellent” quality, with no or minimal venous contamination, without artifacts and homogenous vascular signals, thereby enabling the observer to be highly confident.

The grading of lesion stenosis on CDUS, MRA, and DSA was performed by using an electronic caliper. The sonographer or radiologist determined whether stenosis or occlusion was present in all regions (Figure 2-4). The degree of stenosis was assessed according to a visual grading system: 0 = a completely smooth vessel wall; 1 = < 50% stenosis; 2 = 50–75% stenosis; 3 = 75–99% stenosis; 4 = occlusion (segmental and complete). For analysis purposes, only the most severe stenosis per region was evaluated. Stenoses with a luminal narrowing exceeding 50% were considered to be hemodynamically significant. The stenosis severity of TOF-MRA and CDUS was considered overestimated if the score of stenosis was higher than that found on DSA; otherwise, it was considered underestimated.

Statistical analysis

The Likert scores for the diagnostic image quality are reported as the mean \pm standard deviation and were compared using the paired t test. DSA was considered to be the standard of reference. The whole-region and per-region sensitivities, specificities, positive predictive values (PPVs) and negative predictive values (NPVs) for the detection of significant (50–100%) stenosis are shown as proportions, with corresponding 95% confidence intervals (CIs) and were provided for each estimate. The interobserver agreement with regard to the determination of significant stenosis was evaluated by calculating the k statistic. Cohen's kappa coefficient (κ) was calculated, with $\kappa > 0.80$ regarded as "almost perfect", between 0.61 and 0.80 regarded as "substantial", and between 0.41 and 0.60 regarded as "moderate". $P < 0.05$ (two-sided) were regarded significant. The statistical analyses were undertaken using SPSS v19.0 (IBM, Armonk, NY, USA).

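### The over/underestimation rule has no category for agreement, so as written a TOF-MRA or CDUS score equal to DSA is labelled underestimated

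*Combined protocol and SAP*

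**What the plan says.** The Image analysis section grades stenosis on CDUS, MRA and DSA on one five-level scale, running from "0 = a completely smooth vessel wall" to 4 for an occlusion. The fistula is divided into three regions (inflow, anastomosis, outflow), and each region contributes one score: "For analysis purposes, only the most severe stenosis per region was evaluated".

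One sentence then defines the direction of error against DSA. Severity on TOF-MRA or CDUS is taken as "overestimated if the score of stenosis was higher than that found on DSA; otherwise, it was considered underestimated". There is no term for a score that matches DSA.

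The Statistical analysis section makes DSA the reference standard. It plans a paired t test on the image-quality scores, which use a separate scale. It plans sensitivity, specificity, PPV and NPV "for the detection of significant (50–100%) stenosis are shown as proportions". It also plans a kappa: "The interobserver agreement with regard to the determination of significant stenosis was evaluated by calculating the k statistic". It does not mention over- or underestimation.

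**The concern.** The rule splits every comparison into two classes, but two ordinal scores can stand in three relations: higher, equal or lower. The scale has only five grades, so ties can occur, and they are the outcome that a good index test should produce most often. The rule as written puts all of them in the underestimated class.

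At stake is any statement of the kind that TOF-MRA or CDUS underestimated stenosis in some percentage of regions. Under the literal rule that percentage would rise with the frequency of exact agreement, which is the opposite of what a measure of grading error should do.

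**Working it through.** The plan states no over- or underestimation figure, so there is none to reproduce. The check applies the rule to every possible pair of scores and then derives the size of the effect in general form.

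**Inputs from the documents.** Scores 0, 1, 2, 3, 4; one score per region; DSA as reference; the two-way rule quoted above.

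**Step 1: which pairs are affected.** There are 5 × 5 = 25 possible pairs (index score, DSA score).

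- Index higher than DSA: 10 pairs.
- Equal: 5 pairs (0-0, 1-1, 2-2, 3-3, 4-4).
- Index lower than DSA: 10 pairs.
- Labelled underestimated as written: 5 + 10 = 15. With a separate category for agreement: 10.

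These are counts of possible pairs, not of regions, so they show where the rule goes wrong but not how often. The 0-0 pair is the clearest case: when DSA is 0, no index score can be lower, yet the rule still gives the label. Leaving 0-0 regions out does not close the gap, because the four ties at grades 1 to 4 remain.

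**Step 2: size of the effect.** Let a tabulation contain n regions, of which h score higher than DSA, e equal and l lower, so that n = h + e + l.

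- Underestimated as written: (e + l)/n.
- Underestimated with three categories: l/n.
- Excess: (e + l)/n − l/n = e/n, the share of tied scores in the denominator.
- Overestimated: h/n under both rules.

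If only discordant regions are counted, e = 0 and the excess is zero.

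**Step 3: illustration.** The documents give no scores, so e/n is unknown. The values below are assumptions, with the discordant regions split equally between higher and lower.

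| Assumed exact agreement | Underestimated, as written | Underestimated, three categories | Excess (points) |
|---|---|---|---|
| 50% | 75% | 25% | 50 |
| 70% | 85% | 15% | 70 |
| 80% | 90% | 10% | 80 |
| 90% | 95% | 5% | 90 |

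The last column repeats the first, as Step 2 requires. The table shows the direction and the dependence on agreement; it is not an estimate for this trial.

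**Step 4: do the planned analyses use the label?** Sensitivity, specificity, PPV and NPV depend on whether each method calls a stenosis significant. Kappa depends on whether two observers agree on that call. Neither uses the over/underestimation label, so the change to each is zero.

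**The case against.** The strongest reply is that this is loose wording and not an analysis error. In ordinary usage a grade identical to the reference is neither over- nor underestimated, and calling a 0-0 region underestimated is absurd. A sensible reader would take the sentence to describe the direction of error among scores that differ, and on that reading nothing is wrong. This is probably what was meant. It does not remove the point, because no sentence restricts the rule to discordant scores and someone coding it from the text would include the ties.

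The second reply is that the Statistical analysis section plans no rate, test or interval based on the label. That stands, and it limits the point to a descriptive definition. It also answers a complaint that a reader might add, namely that the denominator is missing. The plan lists no proportion from this label, so the denominator is absent detail for an output that is not planned, and not a separate error.

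The third reply is that any percentages attached to the problem come from assumed agreement rates. That is also correct. Only the identity in Step 2 of the working is established.

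**Conclusion.** The point holds as a minor error in a stated rule. Followed exactly, the rule labels correctly graded regions as underestimated, and nothing elsewhere in the documents corrects it. The size is conditional: if an underestimation frequency is tabulated by the literal rule, it is too high by the share of tied scores in its denominator, which cannot be determined from the documents. It is zero if ties were left out.

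A reader might infer more: that regions in this study were in fact mislabelled, or that the diagnostic accuracy results are biased. The documents support neither. They contain no score data and no underestimation rate, and the accuracy measures and kappa are computed without the label. Confidence is high that the wording has this gap; there is no basis for claiming an effect on any result.

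**What to change.** Replace the two-way sentence with three categories for each modality: overestimated if the score is above DSA, concordant if it equals DSA, underestimated if it is below DSA. If a proportion is reported from these categories, name the regions that form its denominator alongside it.

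The cost is one sentence. If frequencies were already produced with the two-way rule, re-tabulate the recorded scores for TOF-MRA and for CDUS. This needs no new readings and leaves the planned accuracy and agreement analyses as they are.

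### Whole-region accuracy is not defined, and if it pools the three regions of each fistula, its 95% intervals make no stated allowance for within-patient correlation

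*Combined protocol and SAP*

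**What the plan says.** The accuracy results are "The whole-region and per-region sensitivities, specificities, positive predictive values (PPVs) and negative predictive values (NPVs", for detection of significant stenosis with DSA as reference standard. They "are shown as proportions, with corresponding 95% confidence intervals (CIs) and were provided for each estimate" (Statistical analysis). *Whole-region* appears nowhere else. The section names SPSS but no interval procedure, and it mentions no clustering method such as GEE, robust variance or a bootstrap by patient.

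The unit of analysis has to be inferred from Image analysis:

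- "For all participants, the architecture of the AVF was divided into three regions: arterial inflow, anastomosis" and venous outflow.
- "The image quality and diagnostic performance of TOF-MRA were evaluated in all regions".
- "For analysis purposes, only the most severe stenosis per region was evaluated".

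Several lesions in a region are thus reduced to one grade. No corresponding rule reduces three region grades to one result per patient.

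**The concern.** Two readings of the overall result are open: all regions pooled, with up to three observations per patient, or one result per fistula. They are different quantities, so without a definition the reader does not know whether the overall figures describe regions or patients.

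Pooling is the better-supported reading, because a patient-level analysis would need a combining rule and none is given. Keeping one lesion per region removes dependence within a region but not between regions of the same patient. If calls in one patient tend to be right or wrong together, an ordinary binomial interval treats the regions as more independent information than they are and comes out too narrow. The study's overall accuracy would then be reported with more precision than the data hold.

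**Working it through.** The plan states no sample size, expected accuracy or interval width, so there is no figure to reproduce. The check asks how much an unadjusted interval would lose over a range of assumptions.

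**From the documents:** three regions per fistula; one grade per region; 95% intervals; no interval method named.

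**Assumed:** one fistula per patient; 50 or 100 patients; each region diseased independently with probability *p* = 0.4 or 0.6; sensitivity and specificity 0.90; intraclass correlation (ICC) ρ of a correct call from 0 to 0.6; Wilson interval.

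**Step 1: do the two readings differ?** Take region-level sensitivity 0.90, specificity 0.95, region prevalences 10/50/40% and independent errors. For a patient-level rule of any significant stenosis, specificity is 0.95³ = 85.7%. Summing over all disease patterns gives sensitivity 93.8%. The pooled values stay at 90% and 95%, so even the point estimates depend on the definition.

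**Step 2: closed form for the pooled reading.** Only diseased regions count for sensitivity, so the number *m* that a patient contributes varies from 0 to 3. The design effect is DE = 1 + (E[m²]/E[m] − 1)ρ. With *m* binomial(3, *p*), E[m²]/E[m] = (3p(1−p) + 9p²)/(3p) = 1 + 2p, so DE = 1 + 2pρ. The interval should be wider by √DE, and the unadjusted interval covers about 2Φ(1.96/√DE) − 1.

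| ρ | DE (p = 0.4 / 0.6) | √DE | Approximate coverage |
|---|---|---|---|
| 0.05 | 1.04 / 1.06 | 1.02 / 1.03 | 94.5% / 94.3% |
| 0.1 | 1.08 / 1.12 | 1.04 / 1.06 | 94.1% / 93.6% |
| 0.2 | 1.16 / 1.24 | 1.08 / 1.11 | 93.1% / 92.2% |
| 0.4 | 1.32 / 1.48 | 1.15 / 1.22 | 91.2% / 89.3% |
| 0.6 | 1.48 / 1.72 | 1.22 / 1.31 | 89.3% / 86.5% |

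For specificity, exchange *p* and 1 − *p*.

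**Step 3: simulation.** Beta-binomial model, 10,000 replicates per setting, with one patient-level probability of a correct call shared by the three regions. Ranges run over the four measures, both sample sizes and both prevalences.

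| ICC | Coverage of nominal 95% Wilson interval | Extra width of patient-clustered interval |
|---|---|---|
| 0 | 94.8–95.6% | – |
| 0.05 | 94.3–95.0% | 2–3% |
| 0.1 | 93.4–94.6% | 4–6% |
| 0.2 | 92.3–93.8% | 7–11% |
| 0.4 | 89.5–92.0% | 14–21% |
| 0.6 | 86.3–90.0% | 20–31% |

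The closed form agrees closely. For sensitivity with 50 patients and *p* = 0.6, the mean width goes from 12.4 to 13.1 percentage points at ICC 0.1, from 12.3 to 13.7 at 0.2 and from 12.3 to 16.0 at 0.6. A clustered interval (ratio-estimator variance, Wilson form on the effective sample size) covered 92.9–95.6% throughout.

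**Step 4: other disease patterns.**

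- With 70%, 25% and 5% of patients having one, two and three diseased regions, unadjusted coverage is 93.7–95.7% at ICC 0.1, 92.9–95.0% at 0.2 and 89.2–91.9% at 0.6.
- If every patient has exactly one diseased region, *m* = 1 for sensitivity and ICC has no effect on it. Specificity has *m* = 2, so DE = 1 + ρ. Its simulated coverage is 91.2% (50 patients) and 93.5% (100 patients) at ICC 0.2, and 85.5% and 89.5% at 0.6.

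**The case against.** The strongest reply is that the loss needs three things that the text does not establish: that regions are pooled, that the unnamed interval method ignores clustering, and that errors are materially correlated within patients. Silence on method is a reporting gap, not proof of a wrong method. That is correct, and the coverage statement has to stay conditional.

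It can also be said that the effect is small where the ICC is low. At 0.1 the example interval widens by only 0.7 points (12.4 to 13.1), and clear losses need 0.4 or more, which nothing in the documents supports or excludes. This also stands. So does the caution against putting *m* = 3 into the design effect for every measure: at ρ = 0.5 that gives DE = 2.0 and 83.4% coverage, but with mixed disease status fewer than three regions usually enter each measure. For PPV and NPV the result depends partly on the model. With independent patient effects on sensitivity and specificity, the widening at ICC 0.6 falls from about 22–29% to 18–24%.

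The text gives little guidance on the size of the correlation. Having the same readers for everyone does not by itself create within-patient correlation; patient-specific artefact or flow would. Nor do the remarks that "images of each of the four stations were reconstructed in the coronal orientation" and that image quality was graded region by region show that errors are local.

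None of this supplies the missing definition, or makes an unadjusted interval preferable if regions are pooled.

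**Conclusion.** The point holds. That *whole-region* is undefined and that no allowance for clustering is stated are facts of the text. That the intervals are too narrow is conditional on pooling, on an unadjusted method and on positive within-patient correlation. Under the assumptions above, the loss is trivial at an ICC of 0.05, small at 0.1, modest at 0.2 and clear from 0.4 upward. The true size cannot be fixed because the documents give no patient number, prevalence or correlation.

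Pooled point estimates are not affected. Per-region intervals are not affected either, provided each patient has one fistula, which the text does not state. No sample size, threshold or decision rule depends on the whole-region intervals. This is a worthwhile, low-cost improvement to how precision is reported, not a flaw that overturns the study.

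**What to change.** State whether *whole-region* means all regions pooled or one result per patient.

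- **If pooled:** keep the point estimates and compute the four whole-region 95% intervals with the patient as the cluster. Either a bootstrap that resamples patients, or GEE or ratio-estimator robust variance with a Wilson-type interval on the effective sample size, would do. Name the method.
- **If per patient:** state the rule that turns three region grades into one result. No clustering adjustment is then needed.

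The cost is one or two sentences and, only if regions are pooled, a short re-analysis of existing region-level data; the document is dated January 2022, after enrolment ended in March 2021. The downside is usually somewhat wider whole-region intervals. If nearly every patient has exactly one diseased region and the ICC is low, the clustered PPV and NPV intervals can be narrower.
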